10.4.2 Analysis of the Primary Efficacy Endpoint

The primary endpoint is change from baseline in the mean forced vital capacity, measured as the percentage of the age-, height-, gender- and race-adjusted predicted value (FVC-%) over the course of the 18-month treatment period, as reported quarterly (i.e., months 3, 6, 9, 12, 15 and 18). Given that the trajectories of the primary endpoint are expected to differ because of the mechanisms of action of the two treatment modalities, a longitudinal approach incorporating all time points will be employed. Specifically, the endpoint will be analyzed using a linear mixed model with participant-month in the study (3, 6, 9, 12, 15, 18) as the unit of analysis and the change from baseline in FVC-% as the outcome, with terms for baseline FVC-%, treatment group, month, the interaction of month (x) treatment group, and prior MMF therapy (stratification factor: naïve, >0 to \leq 3 months, and >3 months to 6 months), as fixed covariates. Study participant will be treated as a random effect to account for the correlation of outcomes over time within a participant. The model generates adjusted estimates of change from baseline in the FVC-% for each treatment group and month, and an F-test will be used to test the hypothesis that the mean change from baseline during the treatment period differs between the two treatment groups. The model-based adjusted mean change from baseline in FVC-% will be presented graphically by treatment group by study month, with 95% confidence intervals (CIs) provided at each month.

The primary analysis of the primary efficacy endpoint will use the m-ITT analysis set. Appropriate non-linear parametric or non-parametric tests may be applied if the assumptions of the model are not satisfied. Details will be presented in the SAP.

To assess the robustness of treatment effects, a secondary analysis of the primary efficacy endpoint will be performed using the PP analysis set. In addition, two separate *a priori* analyses will be conducted using the model described above with the m-ITT analysis set: one with baseline CT fibrosis scores as a covariate, and one with baseline mRSS as a covariate.

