- **In Scenario 1**, it is assumed that treatment with PFD is associated with an early slowing of the decline in lung function normally observed during the first 3-6 months of cytotoxic therapy and that there is only a small additive effect of PFD to the later improvement in lung function. The collective result is a 2.5% greater response to treatment at 12 months in the experimental versus control arms and this difference between the groups remains the same for the duration of the 18-month study.
- **In Scenario 2**, it is assumed that treatment with PFD is associated with both an early slowing of the decline in lung function and a definite additive effect on the overall improvement in FVC-% that continues throughout the entire treatment period. The collective result is a 3.125% greater response to treatment at 12 months in the experimental versus control arms which continues to slowly increase to a final 3.25% difference between the two groups at 18 months.

**Figure 7.1. Hypothesized Response Trajectories over the 18-Month Double-Blind Treatment Period by Treatment Group with two scenarios considered, all participants naïve to therapy.**

The power to detect a response based on each Scenario was then calculated by carrying out 1,000 clinical trials simulations for each scenario in SAS 9.4, using a linear mixed model with participant-month in the study (3, 6, 9, 12, 15 and 18) as the unit of analysis and the change from baseline in FVC-% as the outcome, with terms for treatment group, baseline FVC-%, month and the interaction of treatment group with month as a fixed covariate and participant as a random effect to account for the correlation of outcomes over time within a participant. (This is a simplification of the model used for the primary analysis of the primary endpoint described above.) We used a compound symmetry variance-covariance structure. The average power is calculated as the number of simulations where the F-test used to test the hypothesis that the mean change from baseline during the double-blind treatment period differs between the two treatment groups is rejected ( $p \leq 0.05$ ) divided by the number of simulations. 95% CIs for power are calculated based on the exact binomial proportion.

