## 10.1 Primary Efficacy Analysis

The primary endpoint is change from baseline in the mean forced vital capacity, measured as the percentage of the age-, height-, gender- and race-adjusted predicted value (FVC-%) over the course of the 18-month treatment period, as reported quarterly (i.e., months 3, 6, 9, 12, 15 and 18). The primary efficacy analysis tests the null hypothesis that the differences between the MMF+PFD and MMF+Plac is zero. The primary analysis of the primary efficacy endpoint uses the m-ITT analysis set. The endpoint is analyzed using a linear mixed model with participant-month in the study (3, 6, 9, 12, 15, 18) as the unit of analysis and the change from baseline in FVC-% as the outcome, with terms for baseline FVC-%, treatment group, month, the interaction of month and treatment group, and prior MMF therapy (stratification factor: naïve, >0 to  $\leq$ 3 months, and >3 months to 6 months), as fixed covariates. Study participant is treated as a random effect to account for the correlation of outcomes over time within a participant.

The model is summarized below.

$$FVC\%-_{it} = \mu_0 + \mu_1 \text{TRT}_i + \mu_2 \text{MONTH}_{it} + \mu_3 \text{TRT}_i \times \text{MONTH}_{it} + \mathbf{x}_i' \boldsymbol{\beta} + \epsilon_{it},$$

where  $FVC\%-_{it}$  is the change of FVC-% from baseline at time  $t$  for patient  $i$  (that is, FVC-% at time  $t$  - FVC-% at baseline),  $i = 1, \dots, 51$ ;  $t = 1, \dots, 6$  (corresponding to 3, 6, 9, 12, 15 and 18 months).  $\text{TRT}_i$  is treatment group (equal to 1 for the PFD and MMF and 0 for Plac and MMF) for patient  $i$ .  $\text{MONTH}_{it}$  is the study month at time  $t$  for patient  $i$ . Two dummy variables for prior MMF therapy (stratification factor: naïve, >0 to  $\leq$ 3 months, and >3 months to 6 months), and baseline FVC-% for subject  $i$  are included in a vector  $\mathbf{x}_i$  of 3 covariates ( $x_1, x_2, x_3$ ) and associated fixed effects are stored in vector  $\boldsymbol{\beta} = (\beta_1, \beta_2, \beta_3)$ . We assume that residual errors  $\epsilon_{it}$  ( $t = 1, \dots, 6$ ) for subject  $i$  are normally distributed with zero mean and 6x6 general/unstructured variance-covariance matrix.

In the context of the primary analysis of the primary endpoint, we are interested in parameter  $\mu_3$ , representing the trajectories of the primary endpoint adjusted for stratifying variables and baseline covariates.

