The model generates adjusted estimates of change from baseline in the FVC-% for each treatment group and month, and an F-test is used to test the hypothesis that the mean change from baseline during the treatment period differs between the two treatment groups.

The model-based adjusted mean change from baseline in FVC-% will be presented graphically by treatment group by study month, with 95% confidence intervals (CIs) provided at each month.

Analysis	Primary Analysis of the Primary Endpoint: mean FVC-% change from baseline during the treatment period differs between the two treatment groups
Analysis Set	mITT Population
Methods	Linear mixed model for repeated measures with correlated errors
Dependent Variable	Change of FVC-% measured at 3, 6, 9, 12, 15 and 18 months (FVC-% at x months – FVC-% at baseline, where x=3, 6, 9, 12, 15 and 18)
Model	Fixed effects: 
 
• Treatment
 
• Study month
 
• Interaction of treatment and study month
 

	
 
• Stratifying variable: prior MMF therapy with 3 categories
 
• Baseline FVC-%
 

Results	
 
• Estimates of mean change from baseline in FVC-% during the treatment period (slope) by treatment group and treatment difference
 
• 95% confidence interval for treatment estimates and treatment difference
 
• P-value for treatment difference
 

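### SAP 10.1 gives the primary model both a participant random effect and an unstructured residual matrix; the random-effect sentence should be deleted and a small-sample correction and a covariance fallback named

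*SAP*

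**What the plan says.** SAP 10.1 describes the model in prose, in an equation and in a summary table.

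- The prose says "Study participant is treated as a random effect to account for the correlation of outcomes over time within a participant". Protocol 10.4.2 says nearly the same ("Study participant will be treated as a random effect to account for the correlation of outcomes over time within a participant") and mentions no unstructured matrix.
- The displayed equation has fixed effects and an error term only, with no participant effect. The six errors per participant are taken as "normally distributed with zero mean and 6x6 general/unstructured variance-covariance matrix".
- The methods row of the summary table reads "Linear mixed model for repeated measures with correlated errors", and the model row lists fixed effects only.
- The parameter of interest is mu3, the treatment-by-month coefficient, "representing the trajectories of the primary endpoint adjusted for stratifying variables and baseline covariates". The results row promises "Estimates of mean change from baseline in FVC-% during the treatment period (slope) by treatment group and treatment difference", which reads as one numeric slope per arm. The same section also promises adjusted estimates for each arm at each month, which suggests categorical month.
- SAP section 7 says of the power simulation: "We used a compound symmetry variance-covariance structure". That is the covariance a random intercept implies.

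The SAP names no degrees-of-freedom method and no fallback covariance. Its list of changes (section 14) does not mention a move from the protocol's random effect to an unstructured matrix.

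**The concern.** The two rules are different models when each is used alone. A random intercept forces equal variances and equal correlations across the six visits. The planning assumptions in SAP Table 7.1 have neither: the SD of change rises from 4.1 to 6.9 and then falls to 6.2, and the correlation falls from 0.866 to 0.780 as the gap between visits grows. A slope contrast is sensitive to exactly that departure, so the random-intercept version can give the named primary parameter a standard error that is too small.

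Used together, the rules are redundant and may bring convergence trouble. The natural response is to drop one component, and the SAP does not say which. The secondary models in SAP 10.2.2 (items 1 to 3) and the PROMIS-29 model in section 12 are defined by reference to the primary model and inherit the same wording.

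**Working it through.** **1. Identifiability.** With participant variance s and residual matrix R, the marginal covariance is V = sJ + R, where J is the 6×6 matrix of ones. An unstructured V has 6×7/2 = 21 distinct elements; adding s makes 22 parameters for 21 quantities. Any shift between s and R that leaves V unchanged leaves the likelihood unchanged. The fixed effects and their model-based standard errors depend only on V, so at convergence they are those of the unstructured model.

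**2. Reproducing the plan's power.** Inputs from SAP Table 7.1: SDs 4.1, 5.1, 6.2, 6.9, 6.2, 6.2; lag correlations 0.866, 0.834, 0.802, 0.790, 0.780; cumulative dropout 6.5, 13, 17, 20, 23, 24%; and the scenario differences. The fitted model was a REML random intercept. The treatment-by-month F-test on 5 df, with categorical month, matches the SAP:

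| Case | SAP | Recomputed |
|---|---|---|
| Scenario 1, 75 per arm | 82.3% | 80.7% (6,000 runs) |
| Scenario 1, 70 per arm | 78.6% | 79.0% |
| Scenario 1, 65 per arm | 76.3% | 76.2% (6,000 runs) |
| Scenario 2, 75 per arm | 95.6% | 95.2% |

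The retained data share also agrees: mean dropout is 103.5/6 = 17.25%, leaving 82.75% against the stated 83%.

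**3. Closed form for mu3 under a random intercept only (numeric month, no dropout).**

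- Centred months m = −7.5, −4.5, −1.5, 1.5, 4.5, 7.5; m′m = 157.5.
- Mean variance = (16.81 + 26.01 + 38.44 + 47.61 + 38.44 + 38.44)/6 = 205.75/6 = 34.29. The mean of the 15 covariances is 414.93/15 = 27.66.
- The within-participant variance the model estimates is 34.29 − 27.66 = 6.63, so its slope variance is 6.63/157.5 = 0.0421.
- The true slope variance is m′Vm/(m′m)² = 1726.2/157.5² = 0.0696.
- Ratio 0.0696/0.0421 = 1.65. Type I error = 2[1 − Φ(1.96/√1.65)] = 12.7%.

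**4. Simulation at the SAP's N of 51** (26/25 assumed, no treatment effect, nominal 5%, random intercept only, model-based standard errors, 10,000 runs, Monte Carlo SE about 0.3 points for mu3):

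| Test | With dropout | Without |
|---|---|---|
| mu3, numeric month | 12.8% | 13.1% |
| Treatment × month, categorical, 5 df | 6.4% | 6.5% |
| Average effect, numeric month | 5.4% | 5.2% |
| Average effect, categorical month | 5.6% | 5.2% |

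At 75 per arm the mu3 figure is 13.0% (2,000 runs), so it is not a small-sample effect.

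**5. Dependence on the true covariance** (same closed form, SAP SDs). Constant correlation, assumed 0.8: ratio 1.08, type I error 5.9%. True AR(1) at 0.866: ratio 2.48, type I error 21.3%. Table 7.1 labels its correlations AR1, but they do not decay that way: 0.866² = 0.750, against the tabulated 0.834.

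**6. Unstructured only** (REML, model-based standard errors, n − 5 df, with dropout). At N = 51, mu3 rejects 8.7% and the average effect 7.7% (2,000 runs; SE for mu3 about 0.6 points). At 75 per arm, mu3 rejects 6.8% and the average effect 5.0% (1,000 runs).

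**The case against.** The strongest reply is that the SAP already settles the matter. Its equation, error assumption and summary table all describe an unstructured repeated-measures model, and the protocol leaves analysis detail to the SAP. On that view the random-effect sentence is a carry-over from the protocol. This largely stands: it is why the conflict should be resolved towards unstructured.

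A reader might infer that the planned primary test has a 13% type I error. The documents do not support that. The figure requires the unstructured matrix to be discarded, month to be coded as one numeric slope, and model-based standard errors to be used. With categorical month or an average-effect test, the same random-intercept fit stays within about 1.5 points of nominal.

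A reader might also infer that fitting both components makes the standard errors depend on the software, or that the analyst is bound to choose after seeing the data. Neither follows: step 1 shows that the redundant intercept leaves the tests unchanged if the fit converges, and the equation already indicates the choice. What remains is the convergence risk and the missing rule for handling it.

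The compound-symmetry simulation is weak evidence of a competing instruction, since SAP section 7 calls it a simplification of the primary model. Nor does the 13% carry over to the secondary outcomes. They inherit the wording, but the calculation uses FVC-% SDs and correlations at six visits, whereas SHAQ and PROMIS-29 have three post-baseline visits and no stated covariance.

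**Conclusion.** The point holds as an inconsistency that should be corrected, with a conditional consequence. One sentence in SAP 10.1, matching protocol 10.4.2, licenses a model under which the mu3 slope test would run at about 13% instead of 5%, within a range of about 6% to 21% depending on the true covariance. The rest of SAP 10.1 favours a model without that fault.

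Removing the sentence does not by itself restore 5%. At N = 51 the unstructured model without a small-sample correction runs at about 7–9% for mu3, so the realistic contrast is about 13% against 7–9%. The missing degrees-of-freedom method matters in its own right.

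These figures assume a 26/25 split, covariates unrelated to outcome, random monotone dropout at the planned rates, and the SAP's planning SDs and correlations as the truth.

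**What to change.** In SAP 10.1:

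- Delete the random-effect sentence. State a repeated-measures model with unstructured within-participant covariance and no random term, and apply the same wording to every secondary and other model defined by reference to the primary.
- Name the Kenward-Roger small-sample correction for standard errors and degrees of freedom.
- Pre-specify what happens if the unstructured fit does not converge: for example, heterogeneous Toeplitz with Kenward-Roger, or a sandwich variance with a small-sample correction. Exclude a random intercept or compound symmetry with model-based standard errors. An uncorrected sandwich variance should not be the fallback at about 25 per arm.
- Record the departure from protocol 10.4.2 in SAP section 14.

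The cost is wording, plus slightly wider intervals from the correction. The performance of Kenward-Roger and of the fallbacks was not simulated here; a short simulation with the Table 7.1 inputs would confirm it.

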## 6 Study Methods

### 6.1 General Study Design and Plan

This study is designed as a phase II multi-center, double-blind, parallel group, randomized and placebo-controlled clinical trial addressing the treatment of patients with active and symptomatic SSc-ILD. Eligibility for the study was assessed during a 3-month screening period. Eligible participants were randomized in a 1:1 assignment to receive either oral MMF and Plac (acting as a control arm) or a combination of oral MMF and oral PFD (acting as an experimental arm), with both regimens administered for 18 months.

MMF was administered orally twice daily with a 4-step titration at monthly intervals to a target dose of 1500 mg twice daily as tolerated. PFD/PBO was administered orally three times daily with a 3-step titration at 2 week intervals to a target dose of 801 mg three times daily as tolerated. Patients could receive ongoing treatment with a maximum tolerated dose for either drug that was less than the target dose according to rules defined by the protocol. MMF is approved for use as an immunosuppressant in solid organ transplantation (cardiac, hepatic and renal) at doses up to 1.5 g twice daily and for the treatment of Lupus nephritis, an autoimmune manifestation of systemic lupus erythematosus, in the dose range of 1 to 3 g daily. PFD is currently approved for the treatment of IPF at a recommended dose of 801 mg (3 capsules of 267 mg each) 3 times daily. They were administered in this study at doses that fall within these FDA-defined dosing ranges but as experimental therapy for SSc-ILD.

A participant was considered to have completed the study if he or she completed all phases of the study including the last visit, or the last scheduled procedure, regardless of the dose of either study drug. Participants were followed in the study even if study drug was prematurely discontinued unless they had withdrawn their consent to do so. End of study was constituted by completion of the entire potential 18 months in all randomized participants.

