## 8.6 Multiple Testing

Statistical testing is conducted at the 0.05 significance level using two-tailed tests; two-sided p-values are reported. No adjustments for multiplicity were planned since there is one primary analysis of the primary endpoint at the end of the study. Secondary analyses of the primary endpoint and analyses of the secondary endpoints serve to assess the robustness of the results and consistency of treatment effect on clinical outcomes important in this disease.

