# 9 Summary of Study Conduct Data

Descriptive summary statistics are tabulated for baseline patient demographics and clinical characteristics, separately by treatment group and overall. Intervention groups are characterized as “MMF+PFD” and “MMF+Plac”. For pooled summaries, “Overall” is used as the column heading. All tables are annotated with the total population size relevant to that table, including any missing observations.

Continuous variables are summarized using descriptive statistics including n, mean, median, standard deviation, range (e.g., minimum and maximum) and using boxplots to examine the distributions of baseline characteristics by treatment group. Qualitative variables are summarized using counts and percentages. Unless otherwise specified, statistical analyses are performed using SAS Version 9 or higher.

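### The primary test of treatment by month names no small-sample correction; run uncorrected in 51 participants, it rejects a true null about 7 to 9% of the time for a linear slope, not 5%

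*SAP*

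**What the plan says.** The primary model in SAP 10.1 is indexed over 51 participants and six visits. Its fixed effects are treatment, month, their interaction, baseline FVC-% and two dummy variables for prior MMF. The residuals "are normally distributed with zero mean and 6x6 general/unstructured variance-covariance matrix".

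On the target, the SAP says: "In the context of the primary analysis of the primary endpoint, we are interested in parameter" mu3, the coefficient on treatment by month, described as "representing the trajectories of the primary endpoint adjusted for stratifying variables and baseline covariates". The Results row of the table in the same section lists "Estimates of mean change from baseline in FVC-% during the treatment period (slope) by treatment group and treatment difference". On the test, "an F-test is used to test the hypothesis that the mean change from baseline during the treatment period differs between the two treatment groups".

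SAP 8.6 sets the level: "Statistical testing is conducted at the 0.05 significance level using two-tailed tests". On software, SAP 9 says only: "Unless otherwise specified, statistical analyses are performed using SAS Version 9 or higher". Neither document states a denominator degrees-of-freedom method or a small-sample adjustment of the standard errors.

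**The concern.** An unstructured matrix over six visits has 6 × 7 / 2 = 21 variances and covariances, here estimated from 51 people, some of whom drop out. The usual model-based standard error of a fixed effect inserts the estimated matrix as if it were known. With 51 participants this makes the standard error of mu3 too small and its p-value too small.

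SAP 8.6 makes no multiplicity adjustment because there is a single primary analysis, so the error rate of that one test matters. Nothing else in the plan checks it. The power simulations in SAP 7 used compound symmetry with 65 to 75 per arm. The sensitivity analyses in SAP 10.2.1 change the population, the covariates or the time point, but not the method of inference for mu3. SAP 10.2.2 (items 1 to 3) and SAP 12 (item 1) reuse the model for other outcomes, so the gap carries over; its size for those outcomes was not computed.

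**Working it through.** **Inputs from the documents.**
- Two-sided 5% level (SAP 8.6); 51 participants and the mean model of SAP 10.1.
- From SAP Table 7.1: SDs of change 4.1, 5.1, 6.2, 6.9, 6.2, 6.2 at months 3 to 18; correlations 0.866, 0.834, 0.802, 0.790, 0.780 at lags of 3 to 15 months; cumulative dropout 6.5, 13, 17, 20, 23, 24%.
- "Eligible participants were randomized in a 1:1 assignment" (SAP 6.1).

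**Assumed.** A 26/25 split, prior-MMF strata of about 60/20/20, dropout completely at random, and the planned SDs and correlations holding in the trial.

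**Step 1: reproduce the plan's own figures.** Power is rejections divided by simulated trials (4,000 per cell), using compound symmetry as in SAP 7. The 5-df treatment-by-month interaction with categorical month matches the stated table to within 2 points:

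| Per arm | Scenario 1, stated | Reproduced | Scenario 2, stated | Reproduced |
|---|---|---|---|---|
| 75 | 82.3% | 81.4% | 95.6% | 95.0% |
| 70 | 78.6% | 78.0% | 92.6% | 94.3% |
| 65 | 76.3% | 76.1% | 91.8% | 92.1% |

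The treatment main effect gives only 52 to 57% in Scenario 1, so the power table rests on the interaction.

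**Step 2: null rejection of linear mu3 (1 df).** REML with an unstructured matrix; between-subject df = 51 − 5 = 46 when all 51 are analysed. Nominal rate 5%.

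| Data | Trials | Chi-square | Residual df | Between-subject df | Satterthwaite | Kenward-Roger |
|---|---|---|---|---|---|---|
| 51 people, planned dropout (258 observations) | 8,000 | 8.9% | 8.8% | 8.2% | 8.0% | 5.5% |
| Same, second run | 6,000 | 8.5% | 8.3% | 7.5% | 7.3% | 5.2% |
| Dropout before month 3 also removed (47 people, 254 observations) | 5,000 | 8.7% | 8.5% | 7.9% | 7.8% | 5.2% |
| 51 people, no dropout (51 × 6 = 306 observations) | 8,000 | 8.1% | 7.9% | 7.4% | 7.5% | 5.6% |

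The Monte Carlo standard error is 0.3 to 0.4 points, e.g. √(0.08 × 0.92 / 8,000) = 0.3 points. A further 1,000 null trials gave 7.0 to 7.5% uncorrected. The inflation is present without missing data, and Satterthwaite barely reduces it because it changes the degrees of freedom and leaves the standard error as it was.

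**Step 3: categorical month.** With planned dropout (4,500 trials), the 5-df interaction rejected 8.3% with between-subject df, 10.6% with residual df and 11.1% with chi-square. Smaller runs with between-subject df gave 8.5% (3,000 trials) and 6.6% (1,614 trials). In the 1,614-trial run Kenward-Roger gave 4.1% for the same test.

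Closed-form check for complete data: five contrasts on 46 error df follow a scaled F(5, 42). The uncorrected rate is P(F(5,42) > F0.95(5,46) × 42/46) = P(F(5,42) > 2.417 × 0.913 = 2.207) = 7.1%.

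**Step 4: the mean-change contrast.** With categorical month and planned dropout, the average-over-months difference rejected 5.6 to 6.2%; across all runs the range was about 4 to 6%. This needs month to be categorical. With linear month, the treatment difference at the average month rejected about 7 to 9% uncorrected, because the estimated matrix then also sets the weights given to the visits.

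**The case against.** The plan is silent; it does not prescribe an uncorrected test. If the analyst requests Kenward-Roger, the SAP as written gives about 5.2 to 5.6%. A reader might infer from the simulations that the planned primary test has an 8% error rate. The documents do not support that, because the rate holds only if ordinary model-based standard errors are used.

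The tested hypothesis is also not settled. The F-test sentence in SAP 10.1 and Protocol 10.4.2 speaks of a difference in mean change over the treatment period. Read as an average over categorical months, that contrast is close to nominal. Against this, SAP 10.1 names mu3, its Results row says slope, and the power table reproduces with the interaction. The mu3 reading is therefore the better supported one, but it remains a reading.

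The exact SAS call cannot be recovered either. SAP 10.1 treats participant as a random effect and also gives an unstructured residual matrix, so the default degrees of freedom are unknown. This prevents naming one figure, but every option without a standard-error correction gave 7% or more for linear mu3.

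Lastly, the excess is 2 to 4 points in a Phase II trial that stopped enrolment early (SAP 14c). That limits the consequence and does not remove it.

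**Conclusion.** The point stands in conditional form. If mu3 is tested as SAP 10.1 indicates, without a small-sample standard-error correction, the null rejection rate is about 7 to 9% for the linear slope and about 7 to 11% for the 5-df categorical interaction, and the 5% of SAP 8.6 is not met. With Kenward-Roger, linear mu3 returns to 5.2 to 5.6%. The average-over-months contrast with categorical month is not materially affected.

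These figures rest on the assumed split, strata shares, planned SDs and correlations, and random dropout. Dropout is not the driver, since complete data still give 7.4 to 8.1%. It would go too far to say that every test from this model is inflated, or that the trial's error rate is known to be 8%.

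**What to change.** Add to SAP 10.1: all mixed models with unstructured covariance use Kenward-Roger adjusted standard errors and denominator degrees of freedom. Refer to that sentence from SAP 10.2.2 and SAP 12, where the model is reused. Naming Satterthwaite instead would not be enough.

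Kenward-Roger does not settle whether month is linear or categorical, or whether mu3 or the mean contrast carries the primary p-value. SAP 10.1 must state that separately.

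The cost is one option in the model call and one sentence. No new data are needed. P-values become slightly larger and confidence intervals slightly wider.

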**Table 7.1.** Power to detect differences in the response pattern from baseline to 18 months for the primary outcome (change in FVC-%) when comparing the course of change in lung function over time for the MMF+PFD arm and the MMF+Plac arm according to the two proposed outcome scenarios. Results assume a 5% two-sided type I error and are provided for three different sample sizes (N = 75/arm; 70/arm and 65/arm)

Assumptions: 
 
- Drop-out rates, variances and data inter-correlations presented below are derived from SLS I and II data and assumed to be identical for the two defined scenarios
 
- A 5% two-sided type I error is assumed
 
- The difference in the outcome measure between treatment arms (relative difference in the change from baseline in absolute FVC %-predicted) for each scenario was estimated based on the hypothetical response to PFD proposed for each scenario as detailed in Figure 7.5.4.
 
				
Scenario 1 Difference between treatment arms (FVC-%)	Scenario 2 Difference between treatment arms (FVC-%)	Dropout (Cumulative %)	SD Estimate	Assumed Correlations (AR1):
Mo 3: 0.5	Mo 3: 0.75	Mo 3: 6.5%	Mo 3: 4.1	3-mo intervals: 0.866
Mo 6: 1.375	Mo 6: 1.75	Mo 6: 13%	Mo 6: 5.1	6-mo intervals: 0.834
Mo 9: 2.25	Mo 9: 3.0	Mo 9: 17%	Mo 9: 6.2	9-mo intervals: 0.802
Mo 12: 2.5	Mo 12: 3.125	Mo 12: 20%	Mo 12: 6.9	12-mo intervals: 0.790
Mo 15: 2.5	Mo 15: 3.25	Mo 15: 23%	Mo 15: 6.2	15-mo intervals: 0.780
Mo 18: 2.5	Mo 18: 3.25	Mo 18: 24%	Mo 18: 6.2	

Power Calculations Scenario 1:				
N per arm at baseline	N per arm at 18 mo	Estimated Statistical Power	95% Lower Bound of Statistical Power	95% Upper Bound of Statistical Power
75	57	82.3%	79.8%	84.6%
70	53	78.6%	75.9%	81.1%
65	49	76.3%	73.5%	78.9%

Power Calculations Scenario 2:				
N per arm at baseline	N per arm at 18 mo	Estimated Statistical Power	95% Lower Bound of Statistical Power	95% Upper Bound of Statistical Power
75	57	95.6%	94.1%	96.8%
70	53	92.6%	90.8%	94.2%
65	49	91.8%	89.9%	93.4%

[figure not shown]
Note that with the given m-ITT design, the linear mixed effects model will actually include data from all subjects who have at least a baseline and one follow-up measure of FVC %. In this setting, even with an overall 24% attrition by the end of 18 months, it is estimated that 83% of the maximal possible study outcome data points (assuming no attrition) would be included in the analysis.

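### SAP 10.1 names two incompatible primary hypotheses, the treatment-by-month coefficient mu3 and the arm difference in mean change, and the power stated in SAP 7 does not settle which one is meant

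*SAP*

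**What the plan says.** SAP 10.1 makes four statements about the primary test.

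- The null: "The primary efficacy analysis tests the null hypothesis that the differences between the MMF+PFD and MMF+Plac is zero".
- The target: "In the context of the primary analysis of the primary endpoint, we are interested in parameter" mu3, which multiplies treatment by month in the model equation.
- The test: "an F-test is used to test the hypothesis that the mean change from baseline during the treatment period differs between the two treatment groups".
- The results row of the summary table: "Estimates of mean change from baseline in FVC-% during the treatment period (slope) by treatment group and treatment difference".

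In the equation MONTH has one coefficient, and treatment has its own separate coefficient, mu1. Yet the section promises adjusted estimates for each month and a "6x6 general/unstructured variance-covariance matrix", both of which suggest that month is categorical. No numerator df is given.

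Protocol 2.2 and 10.4.2 name only the mean-change F-test. Protocol 10.2 defines its parameter as an adjusted mean change trajectory, which fits either reading.

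For power, SAP 7 counts rejections by "the F-test used to test the hypothesis that the mean change from baseline during the double-blind treatment period differs between the two treatment groups". It adds "We used a compound symmetry variance-covariance structure", while the correlation column of Table 7.1 is headed "Assumed Correlations (AR1".

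**The concern.** The p-value that decides the trial depends on which of these tests is programmed. A test of mu3 asks whether the gap between the arms changes over time. The stated null and the F-test sentence ask whether there is a gap. A benefit that is present by month 3 and then sustained lies within the primary hypothesis of faster and/or greater improvement, but it would leave mu3 near zero. If the choice is left open, it could be made after the results are known.

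The ambiguity spreads, because SAP 10.2.2 (items 1 to 3) and SAP 12 (item 1) reuse the same model and the same F-test sentence. The power section should show which test was meant, but it does not.

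**Working it through.** **1. The two hypotheses.** With MONTH numeric, as the equation is written, the arm difference at month t is mu1 + mu3·t. Over visits 3, 6, 9, 12, 15 and 18 the mean month is 63/6 = 10.5, so the mean difference is mu1 + 10.5·mu3.
- mu3 = 0 leaves a constant difference mu1, which can take any value. The arms are parallel, not equal.
- The mean difference can be zero while mu3 is not, when mu1 = -10.5·mu3.

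The outcome has no month-0 record and mu1 is free, so nothing forces the lines to start together. With categorical month, the treatment-by-month test becomes a 5-df test of equal differences across visits, and the same point holds.

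**2. Inputs for power (SAP Table 7.1).** SDs are 4.1, 5.1, 6.2, 6.9, 6.2, 6.2. Correlations at lags of 3 to 15 months are 0.866, 0.834, 0.802, 0.790, 0.780. These are not geometric AR1, since 0.866² = 0.750. Cumulative dropout is 6.5, 13, 17, 20, 23, 24%. Effects:
- Scenario 1: 0.5, 1.375, 2.25, 2.5, 2.5, 2.5; average 11.625/6 = 1.94.
- Scenario 2: 0.75, 1.75, 3.0, 3.125, 3.25, 3.25; average 15.125/6 = 2.52.

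Stated power at 75 per arm is 82.3% (interval 79.8-84.6%) and 95.6% (94.1-96.8%).

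**3. First reading: the lags apply to change scores.** Simulating the compound-symmetry fit with categorical month and no baseline covariate, the 5-df interaction gives about 81% / 96%, inside both stated intervals. The mean-change test that SAP 7 names gives about 56-58% / 78-81%, outside both.

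Analytically, under the planned unstructured covariance, the information is summed over dropout patterns. The SE of the six-visit average difference is 0.916, and the df is 2·75·0.935 - 5, about 135.
- Scenario 1: 1.94/0.916 = 2.11, power about 56%.
- Scenario 2: 2.52/0.916 = 2.75, power about 78%.

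SAP 7 puts baseline FVC-% in the model, but the documents give no baseline-change correlation r. Scaling the variance by 1 - r² gives about 60% / 82% at r = 0.3 and about 68-70% / 88-90% at r = 0.5.

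**4. Second reading: the lags apply to FVC-% values,** as Protocol 10.5.2 item 3 describes. Assume a constant raw SD and an 18-month lag of 0.77, which is not tabled. The correlation of the changes at visits j and k is then (r_jk - r_0j - r_0k + 1) / (2·√[(1 - r_0j)(1 - r_0k)]). For months 3 and 6 this is 0.166 / (2·√[0.134·0.166]) = 0.56; the full range is 0.41 to 0.70. With the tabled SDs and the baseline covariate:
- Mean change: about 73% / 92% (unstructured, analytic) and about 76-77% / 91-92% (compound-symmetry simulation).
- 5-df interaction under compound symmetry: about 48% / 70%.

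**5. Consequence of the choice.** Take 2.5 points at every visit, 75 per arm, first reading. The average gives 2.5/0.916 = 2.73, power about 77%. All between-visit contrasts are zero, so any treatment-by-month test rejects at its 5% level.

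**The case against.** The protocol names only the mean-change F-test, so it can be said that the intended test is clear and that the conflict rests on one SAP sentence and one parenthesis. That stands as a reason to choose the protocol's test. It does not remove the conflict. The SAP is the document that will be programmed, and its summary of changes (SAP 14) neither lists nor withdraws a move to mu3.

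SAP 10.2.1 also plans by-visit differences and a month-18 ANCOVA. These help interpretation but do not fix the primary p-value. Table shells are in a separate document that was not available.

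The constant 2.5-point effect is constructed for illustration. The plan's own scenarios put only 0.5/2.5 = 20% and 0.75/3.25 = 23% of the month-18 difference at month 3.

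A reader might infer from the close match in the first reading that an interaction test was simulated and that true power is 56% / 78%. The documents do not support this. Protocol 10.5.2 says the correlations were measured on repeated FVC-%, and on that reading the mean-change test is the closer of the two. Against that, Table 7.1 stops at a 15-month lag, which is all that six change scores need. Even on the first reading, an undocumented baseline-change correlation of about 0.67 to 0.70 would bring the mean-change test to the stated level.

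**Conclusion.** SAP 10.1 is wrong as written, not merely short of detail. Its stated null and F-test sentence concern the arm difference in mean change, while its named parameter concerns whether that difference varies with time. This follows from the text and needs no simulation. The coding of month and the numerator df are also unsettled.

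The power finding is conditional. At 75 per arm the mean-change test is below the stated figures on both readings worked through. The shortfall runs from 82.3 - 77 = about 5 to 82.3 - 56 = about 26 points in Scenario 1, and from 95.6 - 92 = about 4 to 95.6 - 78 = about 18 points in Scenario 2. Its size depends on what the tabled correlations describe and on the strength of baseline adjustment, neither of which the documents fix. Which test produced the stated power therefore remains unknown.

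**What to change.** In SAP 10.1, make the protocol's test primary: the arm difference in mean change averaged over months 3 to 18, month categorical, 1 numerator df. Equal weighting of the six visits is a proposal; the protocol does not specify weights. Remove or reword the mu3 sentence and the slope label to agree. Report the treatment-by-month test and the by-visit differences as supportive, and carry the wording into SAP 10.2.2 and 12. If treatment-by-month was truly intended, reword the null and the F-test sentence instead.

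Restate power for the chosen test under the planned unstructured covariance, and say whether the tabled correlations apply to FVC-% values or to change scores. If unblinding has occurred, disclose which test gave the primary p-value and report both.

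The cost is SAP wording and a rerun of the power calculation, with no change to data collection. The downside is that, on the readings examined, the restated power for the mean-change test will be lower than the figures now in SAP 7.
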